
The goal of this study is to more fully evaluate the rapid onset of night-time itch and scratch relief following treatment with Crisaborole in comparison to vehicle treatment in children with AD. Moreover, this study will assess the QoL and sleep within the associated caregivers.

Significance

Itch, night-time scratch and sleep are key symptoms experienced by patients with AD and impact not only the patient but the families of the patients with AD, particularly for young age children. Therefore, more fully understanding the cessation of the feeling of itch, action of scratch and improvements in sleep following treatment of Crisaborole (2% BID) would provide additional insight to the treatment profile. This study will specifically evaluate the rapid onset of itch and night-time scratch relief, improvement in sleep (both in the participant and their primary caregiver) and improvement in AD-inflammatory markers following crisaborole therapy twice daily (2% BID) in children 3 months to \leq 11 years old.

This study will also provide critical understanding of the ability of the accelerometry/actigraphy devices to measure drug-induced changes in scratching, movement and sleep quantity in children with symptomatic AD and quality of life in caregivers. It will also provide a physiological comparator for PRO/ObsRO assessments and ultimately enhance understanding of AD.

SCHEDULE OF ACTIVITIES

Period/Visit	Screening	V01 (Baseline)	V02	V03	V04	V05
Day	-28 to -7	-7	1	2	8	15
Window(days)	NA	+/- 3	+/- 3	+ 0.5	+/- 3	+/- 3
ENROLLMENT PROCEDURES						
Informed consent / assent	X	X				
Demographics, medical history including AD history/treatment	X	X				
Inclusion and exclusion criteria Review (both child and caregiver)	X					
Inclusion and exclusion criteria ‡ (both child and caregiver)		X				
Pregnancy test for female caregivers of child-bearing potential		X				
Wide Range Achievement Test 4 (WRAT-4; caregivers only)		X				
MEDICAL PROCEDURES						
Vital signs		X				
Height and weight		X				
ASSESSMENTS						
Investigator's Static Global Assessment (ISGA) (both child and caregiver at V01, only child thereafter)		X	X		X	X
Eczema Area and Severity Index (EASI)		X	X		X	X
% Body Surface Area (BSA)		X	X		X	X
Childhood Asthma Control Test (ages 4 to ≤ 11 years)		X				
Tape Stripping (Biomarker Assessment)**		X		X		X
PATIENT REPORTED/OBSERVER-REPORTED OUTCOMES (PROs/ObsROs)						

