3. STUDY DESIGN

The main objective of this single blind study is to evaluate wearable devices and Observer Reported Itch Assessment in children to assess reduction of itch and night-time scratch in response to Crisaborole treatment vs. vehicle treatment in children with AD. Participants, age 3 months to ≤ 11 years with symptomatic mild to moderate AD, along with their primary caregivers will be recruited and assessed by observed scratch behavior captured from accelerometry/actigraphy.

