Approximately 270 children, age 3 months to ≤ 11 years, and their primary caregiver as participants, for a total of 540 participants (270 pairs), will be randomized in 1:1 ratio to either Crisaborole (2% BID) or vehicle treatment and will be followed for 2 weeks, with an objective of approximately 50% of recruited child participants being ages 5 years old or younger. For this study, we will employ a simple randomization procedure. Participants will be randomly assigned (1:1) using computerized random numbers to receive either crisaborole or the vehicle. The participants will be asked to apply a thin even-layer of Crisaborole 2% or vehicle twice daily (excluding mouth, eyes, and vagina, per label), to all locations with active lesions and record location and time of application on the daily dosing form (as identified on the Dosing Record Sheet, breastfeeding women will be instructed to use the provided gloves when applying crisabrole/vehicle). The study will be comprised of an initial screening/baseline visit for children participants who have an existing diagnosis of symptomatic AD, screened and enrolled in the study along with their primary caregivers after signing an informed consent (or parents/guardians and assent when appropriate). Upon enrollment child participants and caregiver participants will complete a one week acclimation and training phase, where the children will not be on medication, for wearing accelerometry/actigraphy and performing observer-reported outcome assessments (caregivers for participants) and self-reported outcome assessments (caregivers). After the one week acclimation and training phase, the child participants will be on a Crisaborole or vehicle treatment for two consecutive weeks. During those 2 weeks, the children, 3 months up to <2 years will wear one actigraphy or one accelerometry device on each wrist and one actigraphy or one accelerometry device on each ankle (optional for those who have active AD on location of device placement, with a minimum of at least one wrist device needed for enrollment). Children 2 years to ≤ 11 years will wear one actigraphy or one accelerometry device on each wrist (optional for those who have active AD on location of device placement, with a minimum of at least one wrist device needed for enrollment). The primary caregiver (parents/guardians) will also wear one accelerometer device on each wrist and complete daily assessments related to scratching, sleeping habits, pain, AD severity, quality of life, and device comfort questionnaires (parent/guardian will complete as appropriate). The participants will be asked to return to the laboratory

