4. PARTICIPANT SELECTION

This protocol can fulfill its objectives only if appropriate participants are enrolled. Prior to undergoing any study procedures, a participant must meet this protocol's Inclusion/Exclusion criteria.

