4.1. Inclusion Criteria

Both child and caregiver participants must meet all of the following inclusion criteria to be eligible for enrollment into the study:

Children (3 months to ≤ 11 years)

1. Male or female participants aged between ≥ 3 months of age and ≤ 11 years of age at Day -7.
2. Written informed consent from participant/parent(s)/guardian(s).
3. Native English or demonstrated fluency in English (as age appropriate).
4. Participants and parent(s)/guardian(s) are willing and able to comply with study instructions, study visits, procedures, and device placement (devices will be optional for those who have active AD on location of device placement, with a minimum of at least one wrist device needed for enrollment).
5. Have a clinical diagnosis of AD according to the criteria of Hanifin and Rajka.
6. Have AD involvement $\geq 5\%$ Treatable % Body Surface Area (BSA) excluding the scalp and less than 40% BSA.
7. Have an ISGA score of Mild (2) or Moderate (3) at the baseline visit.
8. Have an EASI total score of ≥ 3 at Day -7.
9. Have a minimum Observer Reported Itch Assessment score of 2 at Day -7 (ages 3 months - ≤ 5 years only) or a minimum Patient Reported Itch Severity Scale score of 2 (ages 6 years - ≤ 11 years old) at Day -7.
10. Participant/parent(s)/guardian(s) agrees to refrain from applying diaper rash creams, lotions, ointments, powders, etc. where AD lesions are present, unless AD lesions are present where crisaborole cannot be applied (face within 1 or 2 fingers away from the mouth and hands/fingers).
11. Participants must agree to refrain from applying crisaborole/vehicle to AD lesions on the fingers or hands or within 1 or 2 fingers away from the the mouth to prevent inadvertent ingestion of ointment.

Adult Caregiver

1. Primary caregiver of the child participant, between ≥ 18 years of age and ≤ 75 years of age.
2. Able to understand and cooperate with study procedures and give informed consent.
3. Native English or demonstrated fluency in English.
4. Evidence of a personally signed and dated informed consent document indicating that the participant has been informed of all pertinent aspects of the study.
5. ISGA score of 0 or 1 of AD at the baseline visit, and no reported diagnosis of Atopic Dermatitis.
6. WRAT-4 Word Reading Subtest equivalent to 8th grade reading level or greater.

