5. STUDY PROCEDURES

The study will consist of a screening/baseline (in- laboratory) visit on Day -7 (V01), an in- laboratory visit Day 1 (V02), an in- laboratory visit on Day 2 (V03) for tape-stripping, and Day 8 (V04) for an assessment of the severity of the AD and a final in- laboratory visit on Day 15 (V05) for an assessment of the AD, tape-stripping, completion of ObsROs and return devices. Throughout the study, the participants and caregivers will wear accelerometry/actigraphy devices continuously (optional for those who have active AD on location of device placement, with a minimum of at least one wrist device needed for enrollment; devices may be removed for short periods of time for such things as the purposes of bathing, etc.). Enrolled participants will be randomly assigned to each arm of the study. Participants may come in for an unscheduled visit as needed (i.e., to replace compound, etc.). All in-person study activities, including informed consent and pregnancy testing, will be completed at the Laboratory for Human Neurobiology, [name]. All activities performed in the laboratory are accomplished in private rooms. Primary caregivers will be provided with ample time and a privacy curtain to change into a gown during assessment for exclusion of Atopic Dermatitis, and primary caregivers will accompany children during all activities to ensure participant privacy. All at-home study activities will be completed in the participants' home.

Phone Screening - Day-28 to -7 (~15 minutes):

- Verbal consent (including assent where applicable)
- Assign Participant ID (a sequentially assigned numerical ID used to identify participant on all study documents and in the electronic data capture [EDC] system)
- Screening demographics, medical history including AD history/treatment (includes, race, ethnicity, and gender)
- Eligibility screening (review of inclusion and exclusion criteria)

Baseline Visit 1 (V01)/Day -7 (+/- 3) – In Laboratory (~2 hours):

- Written Informed consent (including assent when applicable)
- Participants are randomly assigned to one of the two arms of the study
- Screening demographics (includes race, ethnicity, gender, and significant medical

history/treatment)

- Pregnancy test for female caregivers of child-bearing potential
- Wide Range Achievement Test 4 (WRAT-4)
- Eligibility Screening (Inclusion/Exclusion criteria)
- Vital signs
- Height and weight

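### Assign arms at V02 (Day 1) rather than V01 (Day -7): a child lost in the untreated week is randomised but contributes nothing to the primary analysis

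*Combined protocol and SAP*

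**What the plan says.** - **When the arm is assigned.** The Section 5 list for Baseline Visit 1 (Day -7, ± 3 days) includes "Participants are randomly assigned to one of the two arms of the study". The Schedule of Activities repeats this as a footnote. Its mark is on the row "Inclusion and exclusion criteria ‡ (both child and caregiver", whose only X is at V01. No section places assignment at V02.
- **What follows.** Section 3 says that "child participants and caregiver participants will complete a one week acclimation and training phase, where the children will not be on medication". Ointment is dispensed at V02 (Section 5, Visit 2, item 11), after nine assessments (items 1-9) and dose application training (item 10).
- **Analysis.** In Section 9 the primary mixed model for change from baseline uses responses from Day 1 (scratch episodes and duration) or Day 2 (ORIA) to Day 15, with baseline as a covariate. Gaps in longitudinal continuous endpoints are left to the model under missing at random. Non-longitudinal continuous endpoints are not imputed. For binary endpoints, anyone who drops out for any reason is a non-responder at all later visits. No analysis set is defined.
- **Eligibility.** Section 4 opens "Prior to undergoing any study procedures, a participant must meet" the entry criteria, Section 5 says "Enrolled participants will be randomly assigned to each arm of the study", and Section 4.1 fixes severity at V01, for example "Have an EASI total score of ≥ 3 at Day -7".
- **Blinding.** Section 3 begins "The main objective of this single blind study is to evaluate wearable devices". Neither it nor any other section says who is blinded.
- **Numbers.** Section 3 has about 270 children and their caregivers, "for a total of 540 participants (270 pairs), will be randomized in 1:1 ratio". Section 9 gives 270 as the number of children to be recruited, from 244 plus about 10% dropout.

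**The concern.** Assignment comes about a week before anything differs between the arms. Losses in that week cannot be effects of treatment, yet they fall after randomisation. They therefore separate the randomised set from the set that informs the primary comparison.

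The plan itself makes such losses foreseeable. Section 8.4 lets families withdraw at any time, including for worsening symptoms, and these are symptomatic children off medication. Device wear starts at V01, and Section 8.4 lets the investigator withdraw a child who cannot tolerate a device. V01 and V02 each have a ± 3 day window. If the windows apply independently (assumption), the nominal 7 days could become 7 + 3 + 3 = 13.

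The plan does not say how such a child is counted, and its rules point in different directions for continuous and binary endpoints. In a trial that does not say who is blinded, it is also worth closing any interval in which an assignment exists but treatment has not begun. Nothing listed before dispensing needs the arm: between V01 and V02 only device wear is listed, and V02 items 1-9 are the same for both arms.

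**Working it through.** **1. The plan's own figure.** Inputs from Section 9: difference 1.0 point, SD 2.6, two-sided 5%, 85% power, 1:1.

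n per arm = 2 × (1.960 + 1.036)² × 2.6² / 1.0² = 121.4, so 122 per arm and 244 in all. Power at 122 per arm is 85.2% (normal) or 84.9% (t). For dropout, 244 / 0.90 = 271.1, so 272; conversely 270 × 0.90 = 243, with power 85.0%. The stated 244, about 85% and about 270 all reproduce.

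**2. Does the timing of assignment affect power?** Let w be the share lost in the untreated week (assumed; not in the documents). The number reaching Day 1 is 270 × (1 − w), whichever visit carries the assignment, so timing drops out. What matters for power is whether the 10% includes w:

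| w | 10% includes w: evaluable, power | w is extra: 270 × (1 − w) × 0.90, power |
|---|---|---|
| 0 | 243, 85.0% | 243, 85.0% |
| 2% | 243, 85.0% | 238, 84.3% |
| 5% | 243, 85.0% | 231, 83.2% |
| 10% | 243, 85.0% | 219, 81.2% |

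Both columns hold for either timing.

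**3. Randomised without entering the primary comparison.** With assignment at V01 this is 270 × w: 5.4, 13.5 and 27 for 2%, 5% and 10%, that is 5, 14 and 27 children. With assignment at V02 it is 0 for losses in that week.

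**4. How the plan would treat a child lost before V02.**

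| Analysis | Treatment under Section 9 |
|---|---|
| Three primary endpoints (mixed model, Day 1 or 2 to Day 15) | No response in the window; adds nothing |
| Other longitudinal continuous endpoints | No response on treatment; adds nothing |
| Non-longitudinal continuous endpoints | Not imputed; absent |
| Any binary endpoint | Could be a non-responder in the assigned arm at every later visit |

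An early-termination visit could yield ratings, but they would predate Day 1. The plan has no rule that moves them into the window.

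**5. Could the comparison shift?** Let a and b be the losses in the two arms (135 assigned to each), and d the gap in ORIA change between lost and retained children. Shift = d × (a − b) / 135. If loss does not depend on the arm, the expected value of a − b is 0 and so is the expected shift. As an illustration only, with d from 1 to 2.6 points (1 SD), which is an assumption:

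| Losses | Split | Shift in points |
|---|---|---|
| 14 | even | 0 |
| 14 | 2:1 (9.3 v 4.7) | 0.03-0.09 |
| 14 | all in one arm | 0.10-0.27 |
| 27 | 2:1 (18 v 9) | 0.07-0.17 |
| 27 | all in one arm | 0.20-0.52 |

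The last row stacks the worst case of every assumption. The formula also takes no account of the baseline covariate, so these are not estimates.

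**The case against.** The strongest reply is that randomising before an untreated run-in is a permissible design and that no harm is demonstrated. That is right. Power is the same, expected bias is 0 if losses do not depend on the arm, and moving the assignment recovers no data: it changes which children count as randomised.

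A reader might infer more than the documents support:

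- **That the arm is known at V01.** No section says it is disclosed then. No ointment is handed over until V02, and Section 8.4 says the vehicle matches the active ointment in appearance, texture, colour and odour. The gap is that the blinded parties are not named. The references to blinded adverse-event reviews in Section 8 do not settle this for raters or site staff, and moving the assignment does not cure it after dosing.
- **That children are randomised before eligibility is checked.** The V01 list has that order, but it is not chronological: devices come last in the list although they are issued straight after consent. Section 4, the reference to enrolled participants in Section 5, and the footnote mark on the eligibility row all point to eligibility first.
- **That the lost child drops out of every analysis.** The non-response rule contradicts this for binary endpoints.
- **That caregiver travel in the untreated week forces withdrawal.** It is an entry exclusion; no section withdraws a caregiver who travels after enrolment.
- **That 270 randomised and 270 recruited conflict.** With assignment at V01 they can be the same children. The distinction matters only once assignment moves.

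It is also true that the change does not make the randomised and analysed sets identical. ORIA enters the model from Day 2, so a child assigned at V02 and lost before Day 2 still has no ORIA response. What survives the reply is the avoidable class of post-randomisation, pre-dose losses and the absence of any rule for them.

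**Conclusion.** The point holds as one about the integrity of the randomised comparison. It concerns neither power nor demonstrated bias. The timing is stated consistently, and the consequence for the primary endpoints follows from the analysis window in Section 9. Its size depends on a pre-dose loss rate that the plan does not give: at 2% to 10% of 270 (assumed), 5 to 27 children would be assigned an arm without contributing to the primary comparison. Any of them could still count as failures in a binary analysis. A shift in the treatment difference arises only if loss depends on the arm, which nothing in the documents shows. The change is worth making because it is cheap and no listed procedure needs the earlier assignment.

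**What to change.** **Preferred change.**

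- Delete assignment from the V01 list in Section 5, and move the schedule's footnote mark from the V01 eligibility row to V02.
- In the Visit 2 list, add 1:1 assignment after item 9 (POEM) and before items 10-11 (dose training and dispensing). It applies to children who met the Day -7 criteria and are still participating. The Day -7 thresholds are not re-applied.
- Define the primary analysis set as all children randomised at V02, by assigned arm. Report by arm any child lost between V02 and Day 2, who would still lack an ORIA response.
- State that about 270 counts children entering V01 and that the 10% dropout covers the untreated week. Reword the sentence in Section 3, and its copy in the synopsis, that has all 270 pairs randomised.
- Separately, state who is blinded.

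**Cost.** One line and one schedule mark move, and a few sentences are added. The simple 1:1 scheme, models, visits and assessments stay as they are. The kit has to be assigned on the dispensing day. No extra families are needed if 270 counts V01 entrants. If it counted children randomised at V02, a 5% to 10% pre-dose loss (assumed) would need 270 / 0.95 = 285 to 270 / 0.90 = 300 families at V01. That is 15 to 30 more visits of about two hours with tape stripping. Each would cost at least $25 + $150 = $175, plus payment for any in-home activities completed.

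**If assignment stays at V01.** State that eligibility is confirmed first, define how never-dosed children count in the continuous and the non-response analyses, state that the 10% covers the untreated week, and report pre-dose losses by arm.

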1. ISGA
2. EASI
3. % affected BSA calculation
4. Children's Sleep Health Questionnaire (CSHQ; ages ≥ 4 to ≤ 11 years) OR BISQ (Brief Infant Sleep Questionnaire; ages 3 months - <4 years)
5. Medical Outcome Sleep Scale (MOS-Sleep; caregivers only)
6. Faces, Legs, Activity, Cry, and Consolability Scale (FLACC)
7. Dermatitis Family Impact Questionnaire (DFI; parent/guardian(s); ages 3 months - ≤ 11 years)
8. Children's Dermatology Life Quality Index (CDLQI; ages ≥ 4 - ≤ 11) OR Infants Dermatitis Quality Of Life Index (IDQOL; ages 3 months - <4 years)
9. Observer-Reported Patient-Oriented Eczema Measure (POEM; ages 3 months - ≤ 11 years)
10. In laboratory dose application training, including weight of the compound or vehicle tube
11. Drug Dispensing
12. Continuous accelerometry wear (Devices will be optional for child participants who have active AD on location of device placement, with a minimum of at least one wrist device needed for enrollment.)
13. Continuous actigraphy wear (Devices will be optional for child participants who have active AD on location of device placement, with a minimum of at least one wrist device needed for enrollment.)

Out-of-Laboratory (At-Home) Assessments (Days 1-15) (~15 minutes per day):

The purpose of the out-of-laboratory assessment is to evaluate wearable devices and ORIA/Patient Reported Itch Severity Scale in a home/routine setting (defined as the participant's routine environment/activities) while the child participant is receiving either crisabole or vehicle. Participants will be provided a fully-charged set of accelerometry devices for use at home.

1. Caregiver to complete ObsRO/PRO measurements as instructed:
 - Observer Reported Itch Assessment (ORIA; ages 3 months- ≤ 11 years)
 - Observer Global Impression of Severity (OGIS; ages 3 months- ≤ 11 years)
 - Peak Pruritis NRS (Caregivers)
 - Patient Reported Itch Severity Scale (Children 6- ≤ 11 years old)
2. At-home dosing (crisaborole or vehicle) in all affected areas except mouth, eyes, and vagina, per label
3. Continuous Accelerometry wear (Devices will be optional for child participants who have active AD on location of device placement, with a minimum of at least one wrist device needed for enrollment.)
4. Continuous Actigraphy wear (Devices will be optional for child participants who have active AD on location of device placement, with a minimum of at least one wrist device needed for enrollment.)

Visit 3 (V03)/ Day 2 (+/- 12 hours) – In Laboratory (~30 minutes):

1. Collect Tape Stripping
2. Weigh tube of compound or vehicle

Visit 4 (V04) / Day 8 (+/- 3 day) In Laboratory (~1 hour):

1. ISGA
2. EASI
3. % affected BSA calculation
4. Children's Sleep Health Questionnaire (CSHQ; ages ≥ 4 to ≤ 11 years) OR BISQ (Brief Infant Sleep Questionnaire; ages 3 months - <4 years)
5. Medical Outcome Sleep Scale (MOS-Sleep; caregivers only)
6. Observer Global Impression of Change (OGIC)
7. Faces, Legs, Activity, Cry, and Consolability Scale (FLACC)
8. Dermatitis Family Impact Questionnaire (DFI; parent/guardian(s); ages 3 months - ≤ 11 years)
9. Children's Dermatology Life Quality Index (CDLQI; ages ≥ 4 - ≤ 11) OR Infants Dermatitis Quality Of Life Index (IDQOL; ages 3 months- <4 years)
10. Observer-Reported Patient-Oriented Eczema Measure (POEM; ages 3 months - ≤ 11 years)
11. In laboratory dose application training, including weight of the compound or vehicle tube
12. Retrieve and re-issue Accelerometry devices (Devices will be optional for child participants who have active AD on location of device placement, with a minimum of at least one wrist device needed for enrollment.)

Visit 5 (V05) / Day 15 (+/- 3 day) or Early Termination (ET)– In laboratory (~2 hours):

The primary purpose of this visit is to retrieve devices and complete end-of-study assessments. In addition, the following procedures will occur.

